#### 4. Fixation

- a. Visual acuity testing in this age group requires a qualitative assessment of fixation and tracking movements of the eyes. The child's attention is drawn to the examiner's or caregiver's face [infants < 3 months] to a hand-held light, toy, or other fixation target.
- b. Fixation behavior is recorded for each eye as "fixes and follows" or "central, steady, and maintained".

Fixation preference graded by the energy the child objects to occlusion of one eye relative to the other eye.

## **Biomarker Blood Samples, Genetic testing and Bio-specimen Sharing:**

### **Biomarker blood samples:**

Serial Blood sample collection will be optional and collected at each subject's enrollment in the study, at the time of the subject's randomization to vigabatrin or placebo (Arm A), at clinical seizures onset, and a final sample after 3 months of seizure control or 3 months of uncontrolled seizures in the open label phase of the study (Arm B). For this group of subjects it will be a total of 4 blood samples over the course of the study. For subjects randomized but remain seizure free on study drug will have three blood samples (at enrollment, randomization and at 24 months of age).

Those subjects who remain seizure free and have a normal EEG will have a second biomarker sample collected at 12 months of age and a final sample at 24 months of age (Arm C). Samples will be stored in the TS Alliance Biosample Repository (a research resource supported by the National Institutes of Health/National Institute of Neurological Disorders and Stroke), for a future research initiative that will test whether we can detect increased mTOR activity and protein synthesis in peripheral lymphocytes from individuals with TSC.

## Genetic testing:

Blood samples from the patient and parents if available will be collected after the subjects' enrollment, and stored at the TS Alliance Central Biobank Repository. DNA will be extracted from these samples and will be used in genetic studies to identify tuberous sclerosis complex disease phenotype modifiers in the future Network collaborative grant proposals. Proposals for sample use will be reviewed by a committee including site PIs and PREVeNT Biorepository Committee which includes a representative from NIH and the TS Alliance. This is optional for subjects and their parents participating in the study and will not impact their enrollment eligibility.

TSC genetic testing will be obtained as part of the clinical diagnostic evaluation of each subject, if it has not already been completed. If the patient's insurance will cover genetic testing of the *TSC1* and *TSC2* genes, this will be done as part of the routine clinical care and will be billed through insurance. If this is not possible DNA samples for those subjects needing testing of *TSC1/TSC2* will be sent to UAB Medical Genomics Laboratory which is a CLIA certified laboratory to undergo genetic testing of *TSC1/TSC2* using next generation sequencing. The DNA will have been extracted and stored at the TS Alliance Central Biobank Repository. The results will be given to the site PI, subject's parent(s)/LAR and entered into the DCC's database.

We will collect the necessary demographic and clinical data information from the human participants for genotype-phenotype analyses and this information will be maintained in the Data Coordinating Center (DCC). We plan to deposit de-identified genotyping data in NIH designated databases (e.g. dbGaP). We will share research data in accordance with NIH and NDAR data sharing policy. Identifiers will be removed from the final data set to fully protect the human participants. We will evaluate each data request to ensure that special circumstances do not exist that would permit anyone to deduce the identification of individuals from the remaining data. If such case exists, we will make the data available under a data-sharing agreement that provides for (1) a commitment to using the data only for research purposes and not to identify any individual participant; (2) a commitment to securing the data using appropriate technology; and (3) a commitment to destroying or returning the data after analyses are completed.

After central extraction/processing, biorepository specimens will be securely labeled, cataloged, and stored according to standard operating procedures appropriate for the specific biosample type and intended future investigations thereof. The TSC PREVeNT Biorepository will utilize liquid nitrogen and/or -80°F freezer cryostorage equipment with automatic emergency electrical backup and a remote notification temperature alarm for long-term storage. Depending on local procedures and capability, permanent preservation of fixed tissues and their storage may be performed locally or shipped for central catalog and storage, as detailed in the study manual of operations. Processing may include receipt and storage of frozen biosamples, centrifugation, separation, aliquoting, labeling and storage, histology/molecular processing, microtomy, and tissue staining for analysis and quality control analysis. Procedures may also include the isolation and quality management of RNA, DNA or proteins, digital imaging of stained

tissue sections, also for quality assessment and/or measurable analysis of small molecules or labeled analytes. In some cases immunohistochemistry or protein profiles may be performed to assess the quality of the fluids or tissues. During all procedures, the biosample identification is managed using barcode labels to reduce transcription error. Biosample identification numbers are unique for each aliquot and are de-identified from any subject PHI.

Acquired specimens of the TS Alliance Central Biobank Repository may continue to be used in accordance with the study protocol and the signed informed consent active at the time the specimens were obtained, even if the subject withdraws consent or fails to complete the entire study. Subjects withdrawing consent from the study and wishing that previously collected specimens be removed from the biorepository must provide written request for specimen removal to the study principal investigator ([name]). The written request for specimen removal should include the subject's name and date of birth, the name of the person submitting the request and relationship to the subject, and the specimen(s) requested to be removed from the TSC Alliance Central Biobank Repository. Upon receipt and verification, we will do our best to remove the requested specimens and associated clinical data from the biorepository and destroy them.

The Data Coordinating Center (DCC) will provide full service electronic data capture (EDC), data management, and reporting services as it currently does for the current TSC-EBS study (P20-NS080199). The extent of these data management services include: database specification, development and testing; validation rules programming; data management plan development and maintenance; ongoing manual data review; and data cleaning and locking. The DCC will implement a quality assurance plan to provide feedback to the clinical sites in order to maintain and improve the quality of the study database. In addition, the DCC will provide statistical analysis and DSMB reports. The PREVeNT Trial Steering Committee will consist of [name] as Study PI, [name] Safety Monitor (MSM), [name], [name] and [name]. The Data Quality Committee will routinely review the monthly data summaries from the trial and monitor the quality and identify any related study issues that warrant a protocol amendment or further analysis or review. NIH will select the PREVeNT Trial DSMB which will review the quarterly DCC reports and communicate with Study PI and MSM.

**Estimate of Key timelines:**

Year 1, Q1/2: Study initiation, implementation of Data Coordinating Center, IEEG.org for EEG data transfer/ storage, and enrollment of subjects 1-4

Year 1, Q3/4: Subjects 5-28 will be enrolled=Total enrollment 28 subjects at the end of Year 1

Year 2, Q1/2: Subjects 29-52 enrolled=total 56 enrolled, Subjects 1-4 complete the 12 month visit

Year 2, Q3/4: Subjects 53-76 enrolled=total 80 subjects, Subjects 5-28- complete 12 month time point

Year 3, Q1/2: Subjects 1-4 reach the 24 month time point and Subjects 29-52 reach the 12 month time point.

Year 3, Q3/4: Subjects 5-28 complete the 24 month time point, Subjects 53-76 reach the 12 month time point

Year 4, Q1/2: Subjects 1-4 reach 36 month time point; Subjects 29-52 reach 24 month time point

Year 4, Q3/4: Subjects 5-28 reach 36 month time point, Subjects 53-76 reach 24 month time point;

\*Analysis begins for the PREVeNT trial using the baseline, 12 and 24 month data set.

Year 5, Q1/2: Subjects 29-52 reach 36 month time point,

Year 5, Q3/4: Subjects 53-76 reach 36 month time point,

\*Analysis will begin for the 36 month developmental assessments and primary and secondary outcome measures.

**Statistical Methods, Sample Size and Analysis Plan:****Monitoring Recruitment**

The table below shows the number screened and the lower limit of a 95% confidence interval for the number randomized. For example, if we screen 10 patients, we expect 6.3 to be biomarker positive (62.5% of the cohort based on the pilot). If the expected is 6.25 (6.3), then if we observe 0 or 1 of the 10 biomarker positive screened who are eligible, we can conclude that the rate of biomarker positivity is statistically likely to be less than 62.5% and we may not reach our target numbers for randomization. The Study and DSMB will monitor recruitment in this manner to enlist early monitoring concerns and discussions of potential solutions, including adding clinical sites or extending recruitment. An analysis of the EEG biomarker data will be done after the first 28 subjects have reached 12 months of age (toward the end of year 2) to estimate whether additional subjects would be needed for Arm A (randomization arm).

Number Screened	Epileptiform Activity	Using Poisson and Normal Approx
	Expected (62.5% screened)	Lower Limit of 95% CI
10	6.3	1.4

15	9.4	3.4
20	12.5	5.6
25	15.6	7.9
30	18.8	10.3
35	21.9	12.7
40	25.0	15.2
45	28.1	17.7
50	31.3	20.3
55	34.4	22.9
60	37.5	25.5
65	40.6	28.1
70	43.8	30.8
75	46.9	33.5
80	50.0	36.1

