**EXCLUSION CRITERIA:**

- 1) Is greater than 6 months of age
- 2) Has not been diagnosed with TSC
- 3) History of seizures or infantile spasms, or evidence of subclinical electrographic seizures on a previous video EEG
- 4) Has received any anticonvulsant medication including vigabatrin, other anti-seizure therapeutic agent including cannabidiol
- 5) Has received an oral mTOR inhibitor such as everolimus or sirolimus
- 6) Has taken an investigational drug, including but not limited to cannabidiol, as part of a research study 30 days prior to enrollment, or plans on taking an investigational drug at any time during the duration of the study
- 7) Is currently enrolled, or plans on enrolling at any time during the duration of the study, in an experimental behavioral early intervention study
- 8) Has a history of being born prematurely (born less than <30 weeks gestation at the time of delivery)

Subjects who have consented and at the time of their baseline study visit and show evidence of electrographic seizures on their initial video EEG will exit from the PREVeNT study and proceed with initiation of management of their clinical condition. All other enrolled subjects will be followed until the age of 36 months with physical and neurologic exams, serial 1-hour awake and sleep video-EEGs, and ophthalmologic evaluation at baseline and defined intervals, every 6-12 weeks based on subjects chronological age.

Study visits and procedures are based on subjects' chronological age in months ( $\pm$ 1 week if under 12 months of age and  $\pm$ 2 weeks if 12 months and older). Once enrolled, subjects enter a 'watchful waiting' protocol which includes baseline EEG at 1.5 month (~6 week) intervals until 12 months of age, then every 3 month (~12 week) intervals until 24 months of age. Subjects will continue in this protocol phase until treatment is justified.

Randomization will be stratified into two groups, according to age at time of emergence of EEG biomarkers: 1)  $\leq$  7 months; 2)  $>$ 7 months of age. This is to account for natural history studies and data from our P20-NS080199 study that indicates mean age of clinical seizure onset less than 7 months of age, with a significant portion of TSC infants developing seizures between 6-12 months and still others after 12 months of age. Accordingly, this randomization strategy will ensure we are able to evaluate age independently of timing of EEG change and treatment randomization.

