### Primary Study Objective:

The primary endpoint of this Phase IIb feasibility trial will be the demonstration of the prevention of seizures and the subsequent cognitive assessment component of the Bayley-III. The other components of the Bayley (receptive communication, expressive communication, fine and gross motor subscores) will be used as secondary and supportive endpoints. The primary goal of this Phase IIb trial will be to provide the evidence needed for a Phase III pivotal trial. Thus, the study will need to demonstrate the purported mechanism by which an improved clinical outcome is achieved, prevention of seizures, leading to a difference in cognitive outcomes. The rationale for not using a composite outcome at this stage of evaluation is that it will be simpler to focus on a single most promising outcome measure of early treatment and one that is clinically meaningful. The other components of the Bayley-III will be evaluated in a multivariate composite as part of the secondary outcomes and exploratory outcome.

The sample size for this feasibility trial is derived from the resources available to support the trial as per this NINDS mechanism, the primary goal of demonstrating a reduction in seizures and the power to assess the differences in cognitive scores on the Bayley-III. To assess the plausibility of recruitment, we looked at the pilot data from our ongoing TSC

Project. To date, we have enrolled 40 patients, 1 patient dropped out; 15 continue without seizures to date; 19 developed well controlled seizures, and 5 have developed refractory seizures. Thus, 25 of the 40 or almost two thirds of the enrolled patients have developed seizures to date. Reducing this number with earlier intervention would seem consistent with achieving a positive effect on the cognitive outcomes as assessed by the Bayley-III.

[figure not shown]
[figure not shown]
[figure not shown]
[figure not shown]
We expect to be able to recruit between 75 and 80 participants over the course of the recruitment period. Based on these numbers we expect 37.5% (based on our P20 data where 15/40 remained seizure free) to be biomarker free and never randomized. Thus, we expect to lose to randomization between 28 to 30 participants yielding approximately 48 patients to be randomized ( $75-28 = 47$  and  $80-30=50$ ) or 24 to 25 participants per group.

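### The recruitment-monitoring table sets biomarker positives seen so far against a cumulative 62.5% rate with no allowance for follow-up, so it leans toward declaring the rate too low when it is on target

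*Combined protocol and SAP*

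**What the plan says.** Monitoring Recruitment introduces its table thus: "The table below shows the number screened and the lower limit of a 95% confidence interval for the number randomized". The expected column is 62.5% of the number screened: "if we screen 10 patients, we expect 6.3 to be biomarker positive (62.5% of the cohort based on the pilot"). In the worked example, "if we observe 0 or 1 of the 10 biomarker positive screened who are eligible, we can conclude that the rate of biomarker positivity" is likely to be under 62.5%. The purpose is early warning: "The Study and DSMB will monitor recruitment in this manner to enlist early monitoring concerns", with more sites or longer recruitment as possible responses. The section adds a separate step: "An analysis of the EEG biomarker data will be done after the first 28 subjects have reached 12 months of age", placed toward the end of Year 2, to judge whether Arm A needs more subjects.

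The statistical Primary Study Objective section explains the complementary 37.5% as "based on our P20 data where 15/40 remained seizure free". The 62.5% is thus cumulative pilot experience to date (and seizure status, used there as a stand-in for the biomarker), not status at screening.

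The text under Exclusion Criteria schedules EEGs every 1.5 months to 12 months of age, "then every 3 month (~12 week) intervals until 24 months of age". It stratifies randomisation by age at emergence, up to 7 months or later. Estimate of Key timelines completes enrolment in the second half of Year 2, then has: "Year 3, Q1/2: Subjects 1-4 reach the 24 month time point and Subjects 29-52 reach the 12 month time point".

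**The concern.** The rule compares two different quantities. The expected value is the share of children who become positive over the whole of surveillance. The observed value is the share already positive when the Nth child has been screened, when recent entrants have had little or no EEG follow-up. A child who will become positive at 9 months but is now 4 months old counts as a shortfall.

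Screened cannot mean that surveillance is finished: on the timeline, no row could then be read before enrolment closed, and the rule could not guide recruitment.

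At stake is the early warning for the roughly 48 randomised children on whom the power statements rest. A rule that can flag an on-target rate does not separate a real shortfall from ordinary waiting time.

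**Working it through.** **1. Reproduce the table.** Lower limit = 0.625N - 1.96 x sqrt(0.625N).
- N = 10: 6.25 - 1.96 x 2.50 = 1.35 (printed 1.4)
- N = 30: 18.75 - 1.96 x 4.33 = 10.26 (printed 10.3)
- N = 80: 50 - 1.96 x 7.07 = 36.14 (printed 36.1)

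All 15 rows agree to rounding. The arithmetic is right; the question is what is compared.

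**2. False-flag chance with full follow-up.** With X ~ Binomial(N, 0.625), P(X at or below the limit) is about 0.1% at every row. It is far below 2.5% because the Poisson variance is wider than the binomial.

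**3. False-flag chance with partial follow-up.** Let f be the share of eventual positives already detected at the look, so X ~ Binomial(N, 0.625f), with the final rate still exactly 62.5%.

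| f | N=10 | N=20 | N=40 | N=80 |
|---|---|---|---|---|
| 1.0 | 0.1% | 0.1% | 0.1% | 0.1% |
| 0.7 | 3% | 7% | 26% | 63% |
| 0.5 | 13% | 37% | 85% | over 99% |

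Any f below 1 raises the chance. That is the direction of the bias, and it needs no assumption about when emergence happens beyond some of it coming after entry.

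**4. Plausible size at 30 screened.** Inputs from the documents: cumulative enrolment of 4, 28, 56 and 80 at 6, 12, 18 and 24 months; the EEG schedule; entry at 6 months or younger; a final rate of 62.5%. Assumed, because not given: entry age uniform on 0.5-6 months; baseline EEG about one week after entry; age at emergence among eventual positives Weibull (shape 1.5, truncated at 24 months). A flag is a count of 10 or fewer among the first 30 children.

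| Median emergence | Counted at 30th enrolment | One week later | Three months later |
|---|---|---|---|
| 3 months | 7% | 4% | 0.4% |
| 4 months | 24% | 16% | 2% |
| 5 months | 46% | 38% | 6% |

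Repeat runs move these by a point or two. At median 4 months, the expected count at the 30th enrolment is 12.4, not 18.8. Counted at the Nth enrolment, medians 3/4/5 give about 7/14/24% at 10 screened and 2.5/8/22% at 80.

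**5. Check with another shape.** Lognormal emergence (log-SD 0.5), counted about one week after each enrolment, gives at least one false flag over the 15 rows in 38% of trials at median 4 months and 74% at median 5. With all emergence uniform between 1.5 and 7 months it is 33%.

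**The case against.** **Size is assumption-driven.** This stands. The documents give no distribution of age at emergence. They put mean seizure onset below 7 months and the commonest onset at 3-7 months, and in Arm A the biomarker precedes the first seizure. Medians of 6 or 7 months therefore fit poorly: under the Weibull model, median 7 implies mean emergence of about 7.8 months, later than mean seizure onset. Those cases give higher rates (roughly 70% and 86% at the 30th enrolment), but they should not be headline figures.

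**The counting date matters as much.** This also stands. The plan states none, and Study Organization and Data Management has the DSMB reviewing quarterly reports. Counting the same 30 children three months later removes most of the effect at medians 3-5. A reader might infer that the rule mainly measures how recently children were enrolled; that is not shown.

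**The analysis of the first 28 children is a safeguard.** In part. It is tied to follow-up and is the step linked to needing more subjects, but it comes when enrolment is nearly complete and does not alter the table. A reader might infer that it counts children who emerge after 12 months as negative. The section gives no method and does not say so.

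**The benchmark is itself immature.** True: the pilot was ongoing. The 62.5% is still cumulative experience, not status soon after entry.

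**The consequence is mild.** True. A signal prompts discussion. It does not stop the trial, change the sample size automatically or touch an efficacy analysis, and the DSMB could allow for age informally.

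One point runs the other way. The simulation has about 53% of children aged 12 months or more at the 80th enrolment; the plan's timeline has subjects 1-28 there, or 28/80 = 35%. The simulated follow-up is more generous than the plan's own.

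**Conclusion.** The concern holds in a limited form. The table has no age or follow-up term, its count is immature at every row on the plan's timeline, and it is biased toward concluding that the rate is below 62.5% when it is on target. At 30 screened, the false-flag chance ranges from 0.4% to about 46% across median emergence of 3 to 5 months and counting dates from the 30th enrolment to three months later, against about 0.1% with full follow-up. Later emergence would raise it. The assumed entry ages, emergence shape and counting date set the size; they do not set the direction.

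The documents do not support reading this as a threat to the primary analysis, or as a demonstrated flaw in the 12-month analysis. It is a miscalibrated early-warning rule that should be corrected because doing so is cheap.

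**What to change.** Replace the expected column with the sum over enrolled children of 0.625 x F(current age), where F(a) is the share of eventual positives expected to have emerged by age a, stated from the P20 data. Compute the lower limit around that sum. Alternatively, keep the table but enter only children past a stated age and use the rate expected by that age. Either way, state the counting date. For the first 28 children at 12 months, state that the estimate will be projected to 24 months.

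In the lognormal scenarios (medians 4-6 months, entry age to 3 or 6 months), an age-adjusted expected count with the same Poisson limit gave false flags of at most about 1.3% per look and 2-4% over all 15 looks.

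Do not tighten the limits alone. The binomial limit at N = 10 is 6.25 - 1.96 x sqrt(10 x 0.625 x 0.375) = 3.25 rather than 1.35; used without a follow-up term, it would raise false flags.

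Cost: wording in the analysis plan and DSMB report, and a short programme using ages and EEG dates already collected. No new visits or subjects. The downside is that the rule says less in the first months, when there is little follow-up to judge.
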